6.1 Intent-to-treat incidence rates of primary efficacy outcomes

All women at all study visits were tested for BV by Amsel criteria, BV by Nugent scoring, TV by wet mount, TV by InPouch culture and vaginal candidiasis by wet mount.

During follow-up, antibiotic and antifungal treatments were given as follows:

- BV was only treated when a woman had BV by Nugent score or modified Amsel criteria but also reported symptoms typical for BV (unusual vaginal discharge, fishy smell) or these were observed by the study physician during a pelvic examination. A diagnosis could almost always be made on the day of the study visit.
- TV was always treated when identified on wet mount or by TV culture. The wet mount results were always available on the day of the study visit, but the InPouch culture results only 5 days later. If a woman had tested negative by wet mount but positive by InPouch culture, she was asked to return to the RU clinic for treatment.
- Vaginal candidiasis was only treated when Candida was present on the wet mount and the participant reported symptoms that are typical for vaginal candidiasis (itching, curd-like discharge) or these were observed by the study physician during a pelvic examination. A diagnosis could almost always be made on the day of the study visit.

We will describe any antibiotic or antifungal use between randomisation and M2 and between M2 and M6 by indication, drug type and drug dosing schedule.

Each positive case during follow-up will be assessed separately to differentiate between incident infections and persistent infections. We will assess whether treatments were dispensed appropriately and whether participants adhered to the treatments.

The incidence of each primary outcome will be defined as follows:

- Incident BV by modified Amsel criteria: positive by modified Amsel criteria after having been negative by modified Amsel criteria at the previous visit or after a case of symptomatic BV (diagnosed by modified Amsel criteria or by Nugent score) was adequately treated.
- Incident BV by Nugent score 4-10: a Nugent score of 4-10 after a Nugent score of 0-3 at the previous visit or after a case of symptomatic BV (diagnosed by modified Amsel criteria or by Nugent score) was adequately treated.
- Incident BV by Nugent score 7-10: a Nugent score of 7-10 after a Nugent score of 0-6 at the previous visit or after a case of symptomatic BV (diagnosed by modified Amsel criteria or by Nugent score) was adequately treated.
- Incident TV by InPouch culture: a positive TV culture after a negative TV culture at the previous visit, or after a case of TV (diagnosed on wet mount or by InPouch culture) was adequately treated.
- Symptomatic vaginal candidiasis: Candida on wet mount plus the presence of symptoms (which the study physician deemed eligible for treatment) after a negative wet mount at the previous visit, a positive wet mount at the previous visit but in the absence of treatment (i.e.no treatment was given), or after adequate treatment for symptomatic vaginal candidiasis.
- In all definitions, one woman can have multiple incident infections, and all of these will be included in incidence rate (IR) and incidence rate ratio (IRR) calculations.

Incidence rates: IRs will be calculated as the number of incident cases per person-days (PD) of follow-up with 95% confidence intervals using the IR function in STATA. IRs will be calculated for each primary endpoint in each of the 4 randomisation groups and for the entire study population. IRs will be calculated for three time periods: between the Enrolment visit and the M2 visit (during product use), between the M2

visit and M6 visit (after cessation of product use) and for the entire study period after randomisation. They will be reported in the following table (one table for each time period):

	Gr	oup 1	Gr	oup 2	Gr	oup 3	Gr	oup 4	Т	otal
	n/N ¹	Cases/PD (IR, 95% CI) ²	n/N¹	Cases/PD (IR, 95% CI) ²						
Incident BV by modified Amsel criteria										
Incident Nugent 4-10										
Incident Nugent 7-10										
Incident TV by culture										
Incident symptomatic vaginal candidiasis										

1. Number of women (n) who developed at least one incident infection during the specified time period as a proportion of the women who had at least one follow-up visit in that time period (N).

2. Incident rate (IR): Number of incidence cases per person-day of follow-up, with 95% confidence intervals (CI).

The median Nugent score and vaginal pH category at each study visit for each study group and the total study population will be visualised using line graphs as follows:

- Nugent score as a count between 0 and 10 (median for the group)
- Vaginal pH as the ordinal categories on the pH strip (median category for the group)

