1.1 Study overview

A flow diagram of study visits, and numbers of women seen at each visit, is shown in Figure 1. Women at high risk for HIV, sexually transmitted infections (STIs), and BV were targeted using community mobilisers who were high risk women themselves. Women who were potentially eligible (HIV-negative, non-pregnant, aged 18-45, and sexually active with high risk of HIV/STI/BV) and interested in participating were invited to visit the RU clinic for screening procedures. Please refer to the study protocol for a full listing of eligibility criteria. At the screening visit, a face-to-face interview, speculum examination, and testing for HIV, pregnancy, urinary tract infection (UTI), BV (by Amsel criteria and Nugent scoring), and *Trichomonas vaginalis* (TV; by wet mount and InPouch culture) were conducted. At the end of the visit, preliminary eligibility was assessed, and initial treatments and referrals were given based on available test results. Additional STI testing was conducted on stored samples after the participant had left the clinic. Results of those tests were given as required, and eligibility was reassessed. At the end of the Screening and Results Visits cascade, women were either declared ineligible or diagnosed with BV by Nugent score and/or TV on wet mount or by culture and treated with 500mg oral metronidazole twice per day for 7 days.

At the Enrolment Visit, only women whose BV/TV treatment had been successful (no BV by Amsel criteria and no TV on wet mount), who were still not pregnant, and who were free of STIs and UTI, were randomised to 4 groups as follows:

Group 1) Behavioural 'vaginal practices cessation and safer sex' counselling only (also referred to as the 'control group');

Group 2) Behavioural counselling plus oral metronidazole 500mg, twice per week for two months; Group 3) Behavioural counselling plus Ecologic Femi vaginal capsule, once per day for 5 days immediately after oral metronidazole treatment followed by thrice weekly for two month;

Group 4) Behavioural counselling plus Gynophilus vaginal tablet, once every 4 days for two months. Participants took/inserted the first dose of their intervention (if applicable) under direct observation at the Enrolment Visit.

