1.2 Visit windows and retention definitions

Visit windows for the study visits were as follows:

- Screening + results visits: the entire screening process should not have taken longer than 6 weeks
- Enrolment visit: maximum of 3 days after completion of oral metronidazole treatment
- Day 7: Day 5 Day 9
- Month 1: ± 7 days
- Month 2: ± 7 days
- Month 6: ± 7 days

The following retention definitions were used:

- Early withdrawal: The participant informed a RU staff member that she no longer wants to participate in the study.
- Late visit: The participant did attend a study visit but after the visit window had closed.
- Skipped visit: The participant did not attend a study visit but did return to the study clinic for a subsequent study visit.
- Lost-to-follow-up: RU does not label a participant as lost to follow-up until study close-out. A participant is considered lost to follow-up at study close-out when multiple contact attempts by RU staff failed (as specified in the RU SOP for Retention) and the participant did also not return to the study clinic spontaneously before study close-out.
- Missed visit: All visits that should have taken place according to the study protocol but did not. This includes all study visits after an early withdrawal or after the last study visit made by a participant who is lost to follow-up, as well as all skipped visits.

2. Primary and secondary clinical endpoints

The endpoints of the study discussed in this SAP are:

Primary clinical objectives	Endpoints
1. To determine the safety of the	- Self-reported solicited and unsolicited (serious) adverse events
three biomedical interventions	(AEs) and social harms
compared to the control group.	 Clinician-observed speculum exam findings
2. To determine the preliminary	– BV by Amsel criteria, Nugent score 4-10* (versus 0-3), TV by
efficacy of the three biomedical	culture and symptomatic vaginal candidiasis at any time during
interventions compared to the	the intervention (Day 7, Month 1, Month 2)
control group in reducing BV	– BV by Amsel criteria, Nugent score 4-10* (versus 0-3), TV by
recurrence without increasing	culture, and symptomatic vaginal candidiasis after cessation of
vaginal candidiasis incidence.	the intervention (Month 6)
	* Abnormal Nugent scores will also be analysed as Nugent score
	7-10 versus 0-6.
Secondary clinical objectives	Endpoints

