6.2 Intent-to-treat incidence rate ratios comparing product use groups to the control group

IRRs with 95% confidence intervals will be calculated comparing each product use group (groups 2-4) to the control group (group 1) using the IR function in STATA. In addition, IRRs with 95% confidence intervals will be calculated comparing each vaginal probiotic group (group 3 and 4) to the metronidazole group (group 2). As before, these IRRs will be calculated for each primary efficacy outcome and for each of the three time periods: between the Enrolment visit and the M2 visit (during product use), between the M2 visit and M6 visit (after cessation of product use) and for the entire study period after randomisation. They will be reported in the following table (one table for each time period):

	Group 2 vs 1 IRR (95% CI)	Group 3 vs 1 IRR (95% CI)	Group 4 vs 1 IRR (95% CI)	Group 3 vs 2 IRR (95% CI)	Group 4 vs 2 IRR (95% CI)
Incident BV by					
modified Amsel					
criteria					
Incident Nugent 4-10					
Incident Nugent 7-10					
Incident TV by culture					
Incident symptomatic					
vaginal candidiasis					

6.3 Per protocol incidence rate ratios comparing product use groups to the control group

A few significant protocol deviations occurred that could have an impact on the primary analysis results:

- CT/NG PCR testing was not available at the RU clinic and was outsourced to the National Reference Laboratory in Kigali, Rwanda. Test results were usually available only weeks after sample collection. We realised that this might be an issue early on and increased the sample size of each randomisation group to 17 instead of 15 to allow for exclusion of women who were randomised while having an ongoing CT or NG infection. Unfortunately, the number of women with a CT or NG infection in each randomisation group turned out to be higher than expected: 8/17 in Group 1, 7/17 in Group 2, 4/17 in Group 3, and 7/17 in Group 4 (Fisher's exact p = 0.53).
- Discrepancy between modified Amsel criteria and Nugent score at the Enrolment visit: Women could be enrolled if they had negative modified Amsel criteria after having completed the 7-day metronidazole treatment. Nugent scores became available later. In a handful of cases, women who were randomised because they no longer had BV by modified Amsel criteria turned out the have a Nugent score of 7-10 at the Enrolment visit.

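### SAP 6.1 lets a BV positive directly after a treated BV episode count as a new case with no negative test in between, so some persistent infections can enter the incidence figures

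*SAP*

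**What the plan says.** SAP 6.1 defines incident BV for three outcomes: modified Amsel, Nugent 4-10 and Nugent 7-10. Each definition has two limbs joined by 'or'. The first needs a negative by the same test at the previous visit. The second applies "after a case of symptomatic BV (diagnosed by modified Amsel criteria or by Nugent score) was adequately treated" and mentions no test result. TV by culture and symptomatic candidiasis have a similar treatment limb. A woman may contribute several incident cases, and all of them enter the IR and IRR.

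Two sentences just before the definitions bear on this. The first is an aim: "Each positive case during follow-up will be assessed separately to differentiate between incident infections and persistent infections". The second is the only content given to that assessment: "We will assess whether treatments were dispensed appropriately and whether participants adhered to the treatments". SAP 6.1 does not define 'adequately treated', and it does not say who makes the assessment or whether that person knows the group.

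Treatment in follow-up is selective: "BV was only treated when a woman had BV by Nugent score or modified Amsel criteria but also reported symptoms typical for BV", or when the physician saw such signs. Scheduled visits are D7, M1, M2 and M6 (SAP 1.1). None is a test of cure after a treated episode.

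**The concern.** The stated objective is BV recurrence. A recurrence needs a cleared infection first, and a completed course does not establish clearance. If a treated woman stays positive and is counted again, failure of the rescue course is mixed with recurrence in the IR, the IRR and the per-period n/N.

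The count also comes to depend on something other than the specimens. Two women with the same slide results get different counts if one had symptoms that led to treatment and the other did not. Protocol 4.4 keeps laboratory readers blind to group but says clinicians cannot be, so the treatment decision brings unblinded information into an endpoint that is otherwise read blind. The pilot is also meant to inform the sample size of a later trial (Protocol 4.3), so the control-arm rate matters beyond this study.

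**Working it through.** The plan gives no event rate or power figure for this definition, so there is nothing to reproduce. The check applies the rule to fixed records and then asks what a repeat positive is likely to be.

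**1. What 'adequately treated' can mean.** If it meant cleared on a test, the second limb would be almost redundant: with no scheduled test of cure, the negative would normally come from a study visit, and the first limb would then apply. The reading that gives the limb work to do is the one 6.1 points to, namely appropriate dispensing and adherence. Elsewhere the wording is closer to an outcome: SAP 1.1 defines successful treatment at entry by negative tests, and SAP 8.1 requires successful treatment before a repeat NG or CT case.

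**2. The rule on fixed results.**
- D7 Nugent 2, M1 Nugent 8, M2 Nugent 8, no treatment at M1: one Nugent 7-10 case (M1).
- Same results, treated at M1 with a full course: two cases (M1 and M2).
- Positive at M2, treated, positive at M6: the woman adds 1 to n in the M2-M6 table. Untreated, she adds 0.

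This is a statement about counting with the results held fixed. It does not say that treatment leaves later specimens unchanged.

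**3. How often a repeat positive might be a failure.** Inputs from Protocol 3.1: 60-80% cured by a standard course, so a failure fraction f of 0.20 to 0.40; about half recurring within six months. Assumptions: a constant recurrence hazard, and failures that stay positive. Then r(t) = 1 − exp(−(ln 2/6)·t), giving r = 0.109 at one month and 0.370 at four. Share of repeat positives that are failures = f / [f + (1 − f)·r].

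| Gap | f = 0.20 | f = 0.40 |
|---|---|---|
| M1 to M2 | 0.20/(0.20 + 0.087) = 0.70 | 0.40/(0.40 + 0.065) = 0.86 |
| M2 to M6 | 0.20/(0.20 + 0.296) = 0.40 | 0.40/(0.40 + 0.222) = 0.64 |

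With recurrence earlier in time (r = 0.25 at one month, 0.50 at four), the shares fall to 0.50-0.73 and 0.33-0.57.

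**4. A lower failure fraction from the trial's own flow.** SAP 3.1 gives 74 women at Enrolment and 68 randomised, so at most 6/74 = 0.081 were turned away for failed treatment, all reasons combined. Putting f = 0.081 into the formula:
- one month: 0.081/(0.081 + 0.919 × 0.109) = 0.45;
- four months: 0.081/(0.081 + 0.919 × 0.370) = 0.19;
- with earlier recurrence: 0.081/(0.081 + 0.919 × 0.25) = 0.26 and 0.081/(0.081 + 0.919 × 0.50) = 0.15.

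First-course failure could be higher than 0.081, because Protocol 6.4 allows re-treatment and later enrolment.

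Across these assumptions the failure share runs from 0.26 to 0.86 at one month and from 0.15 to 0.64 at four. Per 10 treated cases, failures number 10 × 0.081 = 0.8 to 10 × 0.40 = 4.

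**The case against.** **The review.** SAP 6.1 commits to separating incident from persistent infection case by case, so a reader who infers that treatment failures are automatically scored as recurrences goes too far. Non-adherent or wrongly treated women would not qualify, and the review could reclassify others. This stands. However, no rule is given for doing so, and the written definition admits an adherent failure.

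**The term.** SAP 3.3 lists non-adherence and inadequate treatment as separate reasons for not enrolling, which suggests that 'adequately treated' can mean clearance. That shows the term is ambiguous. It does not rescue the second limb, which would then have almost nothing to do.

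**The Enrolment discrepancies.** SAP 6.3 item 2 reports that a handful of "women who were randomised because they no longer had BV by modified Amsel criteria turned out the have a Nugent score of 7-10", at a visit held within 3 days of the course. It is tempting to read this as in-trial proof of failed treatment. It is not: these women were Amsel-negative, which is success by the trial's entry rule. It shows two tests disagreeing, and says nothing direct about rescue courses in follow-up.

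**Direction.** Because treatment depends on discharge or odour, and the Gynophilus leaflet says vaginal products cause discharge, a reader might infer a bias against Groups 3 and 4. The documents do not support that. The same leaflet says controlled release reduces discharge, and the Ecologic Femi sheet does not mention it. Treatment also needed a positive Nugent or Amsel result, and product use stops at M2. Treated cases by arm are not given.

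**True recurrences.** With visits up to four months apart, counting again after treatment is a defensible choice, and dropping those cases loses real events. This stands and shapes the fix.

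**Setting.** This is a descriptive pilot. SAP 6.1 already describes antibiotic use by indication and plots median Nugent score by visit, but neither shows how many incident cases came through the treatment limb.

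**Conclusion.** The concern holds in limited form. The 6.1 definition admits a BV positive directly after a treated positive with no negative in between, and the checks it names cannot identify a completed course that failed. Some persistent infections in treated women can therefore count as incident, while the same results in an untreated woman do not.

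The size is unknown, because the documents do not give the number of treated women who were positive at consecutive visits. The shares in the working depend on background cure and recurrence figures or on a rough limit from enrolment flow, and they should not be read as estimates for this trial. They show only that neither failures nor recurrences can be assumed negligible among such cases. The direction of any effect on the IRR cannot be determined. The GEE models in SAP 6.4 use Nugent status at each visit and are not affected by the incident-case rule.

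**What to change.** Keep the 6.1 count. For each BV outcome, add a row for positives directly after a treated positive, labelled *positive after treatment: persistent or recurrent*, and give IR, IRR and n/N with and without those cases. Do the same for TV and candidiasis, removing only the cases that enter through the treatment limb. For TV this covers nearly every repeat positive, since every detected TV infection was to be treated. Have the incident/persistent classification made from test results and treatment records by someone who does not know the group.

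The cost is a short SAP change and one extra row per outcome, from records already held. The downside is that the count without these cases misses some true recurrences, most of all between M2 and M6, while the count with them includes some failures. The two figures should be read as a bracket. If the IRRs agree, the definition does not matter here; if they differ, the reader can see that the result depends on symptom-triggered treatment.

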AE=adverse event; BV=bacterial vaginosis; CT=*Chlamydia trachomatis*; CVL=cervicovaginal lavage; D7=Day 7 visit; HPV=human papillomavirus; HSV-2=herpes simplex type 2; M1/2/6=Month 1/2/6 visit; NG=*Neisseria gonorrhoeae*; PIN=participant identification number; qPCR=quantitative PCR; STI=sexually transmitted infection; UTI=urinary tract infection; TV=*Trichomonas vaginalis*; VMB=vaginal microbiome.

1. By the algorithm recommended in the most recent Rwandan HIV voluntary counselling and testing guidelines

2. HIV-positive and pregnant women did not undergo a speculum exam unless clinically indicated but they were asked to donate vaginal swabs for VMB assessments.

3. BV (by Nugent) was always treated during the screening process but was only treated when symptomatic and positive by Amsel score at the Enrolment visit and during follow-up. Candida on wet mount was also only treated when symptomatic. TV on wet mount was always treated.

4. For HSV-2 only when negative at baseline.

5. Endocervical swabs were tested for NG/CT by PCR at screening and M6, but may also be tested at enrolment and/or D7/M1/M2 if deemed necessary for clinical reasons or to accurately interpret the VMB findings.

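### SAP 6.1 sets no time at risk for the three BV endpoints, so N and, on the plain reading, person-days include women who cannot be cases; and no analysis compares BV prevalence at Month 6 by arm

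*SAP*

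**What the plan says.** SAP 6.1 defines incidence visit by visit. For Nugent 4-10 a case is "a Nugent score of 4-10 after a Nugent score of 0-3 at the previous visit", or such a score after a case of symptomatic BV was adequately treated. Modified Amsel BV and Nugent 7-10 follow the same pattern. The numerator is also screened by hand: "Each positive case during follow-up will be assessed separately to differentiate between incident infections and persistent infections".

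For the rate, "IRs will be calculated as the number of incident cases per person-days (PD) of follow-up". Footnote 1 to the table gives the proportion of women affected "as a proportion of the women who had at least one follow-up visit in that time period (N"), with no condition that they be free of BV when the period starts.

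BV was not always treated in follow-up. SAP 6.1 requires BV by Nugent or modified Amsel in a woman who also "reported symptoms typical for BV (unusual vaginal discharge, fishy smell) or these were observed by the study physician during a pelvic examination". SAP Table 1, footnote 3, says instead that BV "was only treated when symptomatic and positive by Amsel score at the Enrolment visit and during follow-up".

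Protocol 4.2 and SAP section 2 list BV after cessation (Month 6) as a primary endpoint, and Protocol 4.1 defines preliminary efficacy as incidence. SAP 6.1 and 6.2 plan rates and rate ratios by arm for Enrolment to M2, M2 to M6 and the whole period. SAP 6.1 also plots "The median Nugent score and vaginal pH category at each study visit for each study group". The GEE models in SAP 6.4 take Nugent status at any post-randomisation visit as the outcome.

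**The concern.** Numerator and denominator describe different groups. A woman with untreated BV that persists cannot be a new case, yet she stays in N and, on the plain reading, adds person-days. Between M2 and M6 this lasts for the whole interval, because Month 6 is the only scheduled visit, unless an unscheduled visit intervenes.

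The same holds at the start of follow-up. SAP 6.3 reports that a handful of women "turned out the have a Nugent score of 7-10 at the Enrolment visit". They are removed in the per-protocol repeat but not in the intent-to-treat analysis. Nugent score did not guide enrolment (Protocol 6.3), so women scoring 4-6 at Enrolment could also be randomised. On the plain reading they cannot be incident Nugent 4-10 cases at Day 7, and SAP 6.3 does not list them for removal.

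Two things are at stake. The pilot is meant to inform the sample size of a later trial (Protocol 4.3), and its BV rates may be taken as rates among women at risk. And a product that works during use leaves more women able to become cases after M2, which pushes the M2-M6 ratio upward. Because that ratio omits women still positive from M2, it does not show how many women in each arm have BV at Month 6.

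**Working it through.** No sample-size or event figure exists to reproduce (Protocol 4.3; SAP section 1). The check compares the rules and then sizes the effect.

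**1. Rules side by side.** SAP 8.1 states when time at risk starts for six of its seven outcomes (HIV, HSV-2, syphilis, NG, CT, UTI; not pregnancy), and for NG and CT restarts it when treatment is completed. SAP 6.1 states it for none. The gap matters for the BV endpoints only: TV was always treated, and the candidiasis definition allows a case after an untreated positive wet mount.

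**2. Formula.** Let p be the share with untreated, persisting BV at the start of an interval of d days, and r the risk among the rest. Cases are n(1-p)r. Dividing by all n·d days multiplies the at-risk rate r/d by (1-p). The rate ratio is therefore multiplied by (1-pT)/(1-pC), for product and control.

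**3. Inputs.**
- From the documents: recurrence about 50% within 6 months (Protocol 3.1), giving a hazard of ln2/182 = 0.381 per 100 days; a 57% reduction, reported for twice-weekly metronidazole gel (Protocol 3.1) and used only as an example effect, so rate ratio 0.43 to Month 2; 17 women per arm; 64 seen at Month 6.
- Assumed: visits at days 0, 7, 30, 60 and 182; no effect after stopping; treated women at risk again after 7 days; no spontaneous clearance in the base case; 25%, 50% or 100% of cases untreated. The last is an extreme, since symptomatic BV is treated and women may attend between visits (Protocol 6.8).

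**4. Results (expected values).**

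| Share untreated | 25% | 50% | 100% |
|---|---|---|---|
| Untreated BV at M2, control vs product | 0.053 vs 0.024 | 0.105 vs 0.047 | 0.204 vs 0.094 |
| (1-pT)/(1-pC) | 1.03 | 1.06 | 1.14 |
| M2-M6 ratio, plain reading (at-risk value 1.00) | 1.03 | 1.07 | 1.14 |
| Control whole-period rate per 100 days, plain reading | 0.3095 | 0.2976 | 0.2747 |
| Same cases over at-risk intervals | 0.3248 | 0.3252 | 0.3263 |
| Shortfall from the denominator | 4.7% | 8.5% | 15.8% |

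The shortfall is one minus the quotient of the two rates, for example 1 - 0.2976/0.3252 = 8.5%. With assumed clearance of 10% per month the M2-M6 ratios are 1.03, 1.06 and 1.13; with 25% per month, 1.03, 1.06 and 1.11.

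**5. Precision.** At 50% untreated, expected M2-M6 cases are 6.01 (product) and 5.64 (control). The ratio is 6.01/5.64 = 1.07, with 95% CI 1.07 × exp(±1.96·√(1/6.01 + 1/5.64)) = 0.34 to 3.36. On at-risk time it is 1.00 (0.32 to 3.16).

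**6. Month 6 prevalence.** At 50% untreated and 64/4 = 16 seen per arm, the model gives 40.1% (product) against 43.7% (control): difference -3.6 points, 95% CI -38 to +31. With clearance of 25% per month the difference is close to zero. No direction can be claimed.

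**The case against.** **The text does not say all person-days.** The rate sentence recurs word for word in SAP 8.1 beside explicit time-at-risk rules, so it could mean time at risk in 6.1 too. That stands: for person-days the finding rests on the plain reading of a silent text. For N it rests on an explicit footnote.

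**A post-cessation comparison exists.** A reader might infer that Month 6 is never compared by arm. It is: the M2-M6 rate ratio is planned and rests mainly on that visit. What is missing is a comparison that includes persistent cases. The GEE pools visits with no stated visit-by-group term and has no Amsel model, and the graph shows medians only. Since efficacy is defined as incidence, such a table supplements the plan; its absence is not a departure from the protocol.

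**The sample-size harm is conditional.** If the later trial kept the same visits, treatment policy and case definition, cases per day of total follow-up would be the right planning input. The rate misleads only if read as a rate among women at risk. A reader might also infer a larger understatement by setting the tabled rates against the model hazard of 0.381. Most of that extra gap comes from the lack of an onset-dating rule, not from who is in the denominator.

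**Could an effective product look harmful?** A reader might infer this, since higher assumed hazards (0.3 to 0.6 per month) give M2-M6 ratios of 1.17 to 1.98. Those hazards are roughly 2.6 to 5 times the ln2/6 = 0.116 per month implied by the protocol's recurrence figure, and the documents do not support them.

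**The remedy is imperfect.** It conditions on status after randomisation. With two equal-sized groups of assumed relative hazard 0.2 and 1.8, and 50% untreated, the M2-M6 ratio is 1.13 on the plain reading and still 1.06 on at-risk time.

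**Conclusion.** The point holds, as a minor one. For the three BV endpoints the case rule is conditional on being BV-free or treated, N is not, and person-days on the plain reading are not. At 25-50% untreated, the control whole-period rate is about 5-9% low as a rate among women at risk, and the M2-M6 ratio moves from 1.00 to about 1.03-1.07. That shift is negligible beside a roughly ten-fold confidence interval in a descriptive pilot and would not change its conclusions.

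The sizes rest on an assumed untreated share, the protocol's recurrence figure and no effect after stopping. If untreated BV at Month 2 is equally common in both arms, the M2-M6 ratio is not distorted at all. The number of women positive by Nugent at Enrolment is not given beyond a handful at 7-10, so their contribution cannot be sized. Separately, no planned analysis shows by arm how many women have BV at Month 6.

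**What to change.** 1. In SAP 6.1-6.3, for the three BV endpoints, count person-days only over intervals that begin with a negative result for that endpoint or after completed adequate treatment. Set N to women at risk in at least one interval of the period. State one onset-dating rule, for example the midpoint between visits. Label the M2-M6 ratio as conditional on being BV-free or treated at Month 2, a post-randomisation status, so that the change is understood to reduce the distortion without necessarily removing it.
2. As a supplement to the incidence analysis, add one table of the number and proportion positive at Month 6 by randomised arm among all women seen, for each BV endpoint, with a risk difference and 95% CI. Record when it was added, because SAP 3.1 already reports Month 6 attendance.
3. Reconcile the BV treatment triggers in SAP Table 1, footnote 3, and SAP 6.1, since they determine how much BV stayed untreated.

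The cost is SAP wording, one small table and a few lines of code; the visit results and dates are already collected. The downside is fewer person-days (control M2-M6 from 17 × 122 = 2,074 to about 1,507 at 50% untreated with midpoint dating), hence higher and less precise absolute rates. Case counts do not change, so neither does the relative width of the rate-ratio interval.
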